6.2. Number of Subjects

18 Children 1 to 17 years of age, inclusive. Each subject will receive ceftaroline. 2 subjects above 5 years old will be enrolled before the younger subjects are enrolled.

Based on A'Hern's single-stage design for Phase II clinical trials 18 subjects would be required to reject $H_0: \pi \leq 0.50$ and conclude $H_1: \pi \geq 0.80$ with 80% power assuming a Type 1 error rate of 0.05.

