7.8. Premature Discontinuation From Study Drug Administration

7.8.1. Discontinuations Due to Safety

Assessments and Procedures: A subject who is prematurely discontinued from study drug administration (ie, before the anticipated full course of study drug required for effective treatment of hematogenous SA osteomyelitis *for safety reasons*) should have EOIV or EOT (if on PO drug) assessments conducted per Section 9, and undergo subsequent assessments at FU, if possible. The same procedures will be followed if the subject needs to continue home IV therapy to complete treatment because the subject is intolerant of an appropriate oral antibiotic or there is no oral agent that is active against the organism isolated.

Clinical Outcome Assessment:

If a subject prematurely discontinues the study drug due to an SAE and requires alternative non-study antimicrobials for hematogenous SA osteomyelitis, the subject should be assessed indeterminate.

Reasons: Reason(s) for premature discontinuation from study drug administration *due to safety* may include, but are not limited to, the following:

- Occurrence of an SAE that, in the opinion of the Investigator, warrants the subject's permanent discontinuation from the study drug or oral drug administration.
- Known pregnancy or breastfeeding during the drug administration period. A female subject whose pregnancy test is positive at the end of total treatment must be followed through the immediate postnatal period or until termination of the pregnancy. Every pregnancy will be reported as soon as possible (within 24 hours of learning of the pregnancy), as described in Section 11.1.4.

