7.8.2. Discontinuations Due to Insufficient Therapeutic Effect

Assessments and Procedures: A subject who is prematurely discontinued from study drug administration *due to insufficient therapeutic effect* should have EOIV (if on IV study drug) or EOT (if on PO drug) assessments conducted per Section 9, and undergo subsequent safety assessments at the 4 to 6 week follow up visit. If a subject is discontinued from IV study drug administration *due to insufficient therapeutic effect* and is switched to an alternative IV antibiotic, the alternative therapy should be recorded.

Clinical Outcome Assessment: A subject who is prematurely discontinued from study drug administration *due to insufficient therapeutic effect* should be assessed as a clinical failure on the day of discontinuation. Such a subject will be automatically assigned an outcome of clinical failure at all subsequent evaluation time points.

Reasons: Reason(s) for discontinuation from study drug administration *due to insufficient therapeutic effect* may include, but are not limited to, the following:

- Clinical Worsening: A subject who shows signs of clinical worsening may be prematurely discontinued from study drug administration at any time. If the Investigator deems the benefit-to-risk ratio of continuing study drug acceptable, study drug administration for at least 48 hours is encouraged before discontinuation. If the subject is improving clinically but the blood cultures are persistently positive for *S. aureus* for up to 5 days, ceftaroline can be continued at the discretion of the investigator.
- Lack of Clinical Progress: For a subject who is stable, yet does not show signs of improvement, the Investigator is encouraged to continue study drug administration at least 48 hours before such a subject is assessed as a clinical failure and the subject is prematurely discontinued from study drug.

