7.10. Stopping Rules

The incidence or severity of AEs indicates a potential health hazard to subjects. The study will be stopped if treatment failures occur in two patients or severe adverse events that are due to ceftaroline in the opinion of the PI occur in two patients.

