12.3. Secondary Endpoints

1. Successful treatment of acute hematogenous osteomyelitis at one year after completion of a 4 to 6 week total antibiotic treatment and at one year after enrollment.
2. Clearance of *S. aureus* bacteremia if blood cultures initially positive.
3. The proportion of children with plasma concentrations of ceftaroline that exceed 1 μ g/mL for over 60% of a dosing interval.

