12.7. PK Analysis

The mean and median concentrations of ceftaroline in plasma at the end of infusion will be determined. The proportion of children with plasma ceftaroline concentrations $\geq 1 \mu\text{g/mL}$ at 4 hours after infusion will be determined.

The plasma levels of ceftaroline obtained at 4 hours after the end of a 2 hour infusion will be compared to the ceftaroline MIC for the *S. aureus* isolate recovered causing the osteomyelitis. Ideally, the plasma level should exceed the MIC at this time point which would be for at least 75% of a dosing interval. Assuming the patients do well clinically, there will be no adjustment of the dose even if the target concentration is not achieved at the 6 hour time point following the start of ceftaroline infusion. However, if two subjects do not improve as anticipated, the study will be halted and plasma levels compared to the MICs of the causative *S. aureus* isolates. If plasma levels exceed the MIC and yet the subjects are considered treatment failures in that they are not responded as expected, the investigator would conclude that ceftaroline may not be particularly effective in treating *S. aureus* osteomyelitis in children. If the plasma levels at this time point are below the MIC, a dose modification may be considered but the investigator may decide that studying ceftaroline for this indication is no longer necessary.

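### The 80% power in Section 6.2 leaves pi undefined and ignores the two-failure stop in Section 7.10, and Sections 7.10 and 12.7 differ on what follows the second failure

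*Combined protocol and SAP*

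**What the plan says.** - Section 6.2 uses A'Hern's "single-stage design for Phase II clinical trials 18 subjects would be required to reject" pi at or below 0.50 and conclude pi at or above 0.80, with 80% power and type I error 0.05. It gives no cutoff, does not define pi and does not mention early stopping. The primary endpoint in Section 12.2 is safety.
- Section 7.10: "The study will be stopped if treatment failures occur in two patients or severe adverse events that are due to ceftaroline", the latter also at two patients and in the investigator's opinion. No restart is mentioned.
- Section 12.7: "if two subjects do not improve as anticipated, the study will be halted and plasma levels compared to the MICs" of the causative isolates. If plasma levels exceed the MIC and the children still fail, the investigator would conclude that the drug may not be particularly effective. If levels are below the MIC, "a dose modification may be considered but the investigator may decide that studying ceftaroline for this indication is no longer necessary".
- On who is a failure, Section 7.8.2 says a child taken off study drug for insufficient effect "should be assessed as a clinical failure on the day of discontinuation". Section 7.8.1 says that a child who stops because of an SAE and "requires alternative non-study antimicrobials for hematogenous SA osteomyelitis, the subject should be assessed indeterminate". Section 7.8.3 treats withdrawals not already assessed as failures in the same way.
- On timing, Section 12.3 lists "Successful treatment of acute hematogenous osteomyelitis at one year after completion of a 4 to 6 week total antibiotic treatment", and also success at one year after enrolment.

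**The concern.** A single-stage test presumes that all 18 outcomes are observed. A stop at the second treatment failure is a sequential rule that can prevent this. The alternative in Section 6.2 allows for 20% non-success, an expected 0.20 × 18 = 3.6 children, yet two of these are enough to stop the study if they are classed as treatment failures.

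The power statement is the only quantitative argument for 18 children. If it does not survive the protocol's own stopping rule, readers and the ethics board are given a design property that the study may not have. They are also not told how likely it is that the primary safety dataset will be smaller than 18. In addition, whoever has to act on a second failure finds two different descriptions of what happens next.

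**Working it through.** **Reproducing the plan's figure.** Inputs from Section 6.2: null 0.50, alternative 0.80, alpha 0.05, power 80%. For each n, take the smallest cutoff r with P(X ≥ r | n, 0.50) ≤ 0.05:

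- n = 16, r = 12: power 0.798
- n = 17, r = 13: power 0.758
- n = 18, r = 13: alpha = P(X ≥ 13 | 18, 0.50) = 0.048; power = P(X ≥ 13 | 18, 0.80) = 0.867

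So 18 is the smallest size that meets both targets, and the rule tolerates 18 − 13 = 5 non-successes.

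**Adding the stop.** Assumptions, none of them settled by the documents:

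1. pi is clinical success, with true value 0.80.
2. The stop is final.
3. Indeterminate children count as non-successes in a denominator of 18.
4. A share s of non-successes are treatment failures. The documents give no value, so a range is shown.
5. The severe-adverse-event part of Section 7.10 is left out.

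Each child is then a success (0.80), a treatment failure (0.20·s) or another non-success (0.20·(1 − s)). Let m be the number of children whose failure can be known in time to stop the study:

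Power = P(at least 13 successes in 18, and at most 1 failure among the first m)

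- *Immediate:* failure is known before the next enrolment, so m = 17. With m = 18, a second failure in the last child also blocks the conclusion.
- *One year:* at the 6 children per year given in the Summary, enrolments are about 61 days apart. A failure known 365 days after enrolment is available before the 18th enrolment for 12 children (6 × 61 = 366 days). If it is known a year after a six-week course (365 + 42 = 407 days), that falls to 11 (7 × 61 = 427). So m = 12 or 11.
- *Variant for both:* a stopped study may still claim success if 13 successes are already among the enrolled children.

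Hand check at s = 1, m = 17: at most one failure among 17 already guarantees at least 16 successes, so power = 0.8^17 + 17 × 0.2 × 0.8^16 = 0.0225 + 0.0957 = 0.118.

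| Case | s = 100% | s = 50% | s = 25% | Break-even s for 80% power |
|---|---|---|---|---|
| Immediate, m = 18 | 0.099 | 0.439 | 0.709 | 15.1% |
| Immediate, m = 17 | 0.118 | 0.467 | 0.723 | 16.0% |
| Immediate, 13 successes count | 0.198 | 0.518 | 0.741 | 17.3% |
| One year, m = 12 | 0.275 | 0.620 | 0.789 | 22.9% |
| One year, m = 11 | 0.321 | 0.651 | 0.800 | 25.0% |
| One year, 12 known, 13 successes count | 0.378 | 0.664 | 0.802 | 25.5% |
| One year, 11 known, 13 successes count | 0.427 | 0.693 | 0.813 | 28.2% |

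Multiplying the break-even share by 0.20 gives the proportion of all children: 3.0% to 3.5% (immediate) and 4.6% to 5.6% (one year).

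**Chance of stopping before the 18th child,** 1 − (1 − q)^m − m·q·(1 − q)^(m−1) with q = 0.20·s, at s = 100% / 50% / 25%: 88% / 52% / 21% for m = 17, and 68-73% / 30-34% / 10-12% for m = 11 or 12. For m = 17, expected enrolment at s = 100% / 50% is 9.4 / 14.0 children.

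**Type I error.** At pi = 0.50 the probability of rejection stays at or below 0.048 in every case, because the stop only removes chances to reject.

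**Sections 7.10 and 12.7 side by side.**

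| | 7.10 | 12.7 |
|---|---|---|
| Efficacy trigger | two treatment failures | two children not improving as anticipated |
| Severe-adverse-event trigger | yes | not mentioned |
| Consequence | stopped; no restart stated | halted; MIC comparison; possible dose modification or end of study |

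**The case against.** The strongest reply is that the thresholds rest on readings the protocol does not supply. If pi is a safety or pharmacokinetic proportion, the calculation does not apply. If the study resumes after a halt, as Section 12.7 allows, the loss may be nil. Section 12 plans descriptive analyses and no hypothesis test, so no planned conclusion would be wrong. The safety set is every child dosed, which remains valid after a stop, and a smaller dataset is the ordinary price of a protective rule. All of this stands. It limits the harm to a misleading design figure and an unstated risk of fewer safety data. It does not supply the missing definition of pi or the missing link between Sections 6.2 and 7.10.

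It is also fair to say that the two efficacy triggers may be meant to coincide: Section 12.7 itself writes that "the subjects are considered treatment failures in that they are not responded as expected", and it can be read as explaining what follows a stop under Section 7.10. A reader might infer a flat contradiction on the trigger, but the text does not establish one. What does differ is the consequence.

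Two other strong readings are tempting. One is that the true power is only about 10-20%. That needs every non-success to be a treatment failure known at once, whereas Sections 7.8.1 and 7.8.3 provide for children who are indeterminate instead. The other is that 18 is the wrong number or that alpha is inflated. The 18 reproduces, and the stop can only lower the rejection probability.

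**Conclusion.** The concern holds in conditional form and should be fixed. The 80% in Section 6.2 describes a test on all 18 children for an unnamed endpoint, and it takes no account of the two-failure stop. Under the assumptions listed, it survives only if treatment failures are no more than about 15-17% of non-successes with immediate knowledge of failure, or about 23-28% if failure is known only at one year. The upper end of the one-year range requires that 13 successes reached before the stop count. At failure shares of 100% / 50% / 25%, power is 10-20% / 44-52% / 71-74% (immediate) or 27-43% / 62-69% / 79-81% (one year). The documents do not say where in these ranges the study lies, so no single corrected power can be given. Confidence in the size is therefore medium. The omission itself, and the difference between Sections 7.10 and 12.7 on what follows the second failure, can be read directly from the text.

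**What to change.** In Section 6.2, do one of the following:

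1. Name the endpoint that pi refers to, state the rule of at least 13 of 18 and how indeterminate children count, and restate the power with Section 7.10 in force. Show the assumed failure share, when failure is known and whether the stop is final.
2. Withdraw the power claim and justify 18 children by precision for the primary safety objective. With no events in 18, the two-sided 95% upper limit is 1 − 0.025^(1/18) = 18.5%. The chance of seeing at least one event with a true rate of 5% / 10% is 1 − 0.95^18 = 60% / 1 − 0.90^18 = 85%. Add figures for illustrative early stops: the upper limit is 23.2% for 0/14 and 33.6% for 0/9.

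Reconcile Sections 7.10 and 12.7 on what follows the second failure, and use one wording for the efficacy trigger. This review does not say which rule is right.

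The cost is protocol wording and a power figure that is conditional or less favourable, or its replacement by precision. No extra patients are needed.

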7.9. Replacement of Subjects

Subjects who are withdrawn from study before receiving any amount of study drug will be replaced in order to enroll a total of 18 treated subjects for safety evaluations. Subject numbers will not be reused.

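### Section 6.2 treats rejecting π ≤ 0.50 as concluding π ≥ 0.80; with 18 children rejection shows only π > 0.50, and 0.80 is just the rate at which power was computed

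*Combined protocol and SAP*

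**What the plan says.** Section 6.2 (Number of Subjects) justifies the sample size in one sentence. It opens "Based on A'Hern's single-stage design for Phase II clinical trials", continues "18 subjects would be required to reject $H_0: \pi \leq 0.50$ and conclude $H_1: \pi \geq 0.80$ with 80% power", and ends "assuming a Type 1 error rate of 0.05". It gives no cut-off, does not say whether the error rate is one- or two-sided, and does not say which proportion π is.

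No other section supplies these. Section 12.2 makes safety the primary endpoint without defining a rate. Section 12.4 describes descriptive safety summaries. Section 12.5 lists the efficacy outcomes with no test, interval or success criterion. Section 7.9 ties the 18 to safety: never-dosed subjects "will be replaced in order to enroll a total of 18 treated subjects for safety evaluations".

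Two other places bear on the point. Section 7.10 stops the study if two patients are treatment failures, and Section 12.7 halts it if two subjects do not improve as expected.

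**The concern.** A single-stage test has one null value, here 0.50. Its error rate is controlled at that value and below, so rejection is evidence that π exceeds 0.50. The value 0.80 enters only when power is calculated. Section 6.2 instead makes π ≥ 0.80 what is concluded on rejection and attaches the 80% power to that conclusion. Rates between 0.50 and 0.80 belong to neither stated hypothesis, so rejecting the first does not establish the second.

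At stake is what an uncontrolled study of 18 children may claim. Above one half and at least four fifths are very different statements, and this sentence is the plan's only account of what a formal result on π would mean.

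**Working it through.** **Inputs, all from Section 6.2:** n = 18, null rate 0.50, design rate 0.80, power 0.80, Type 1 error 0.05. Assumption: the error rate is one-sided, because the null is π ≤ 0.50.

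**1. Reproduce the plan's figure.** Find the smallest n with a cut-off r such that P(X ≥ r | n, 0.50) ≤ 0.05 and P(X ≥ r | n, 0.80) ≥ 0.80, with X binomial. For n = 18:

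| Cut-off r | P(X ≥ r) at 0.50 | P(X ≥ r) at 0.80 |
|---|---|---|
| 12 | 0.119 | 0.949 |
| 13 | 0.048 | 0.867 |
| 14 | 0.015 | 0.716 |

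Only r = 13 meets both conditions. By hand, P(X ≥ 13 | 0.50) = (8568 + 3060 + 816 + 153 + 18 + 1)/2^18 = 12616/262144 = 0.0481. The search confirms that 18 is the smallest such n. At one-sided 0.025 it would be 20 (cut-off 15), so the stated 18 fits one-sided 0.05.

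**2. What each result excludes.** The one-sided 95% exact (Clopper-Pearson) lower bound L solves P(X ≥ x | 18, L) = 0.05. The p-value against π ≤ 0.80 is P(X ≥ x | 18, 0.80).

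| Result | Observed rate | Lower bound L | p against π ≤ 0.80 |
|---|---|---|---|
| 13/18 | 0.722 | 0.502 | 0.867 |
| 14/18 | 0.778 | 0.561 | 0.716 |
| 15/18 | 0.833 | 0.623 | 0.501 |
| 16/18 | 0.889 | 0.690 | 0.271 |
| 17/18 | 0.944 | 0.762 | 0.099 |
| 18/18 | 1.000 | 0.847 | 0.018 |

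Checks by hand: for 18/18, L = 0.05^(1/18) = 0.847. For 17/18, p = 0.8^18 + 18 × 0.8^17 × 0.2 = 0.018 + 0.081 = 0.099.

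At 13 and 14 successes the test rejects although the observed rate is itself below 0.80. Only 18/18 excludes 0.80 and below at one-sided 5%. Other methods agree that 17/18 falls short: the Wilson lower bound is 0.785 and the mid-p value 0.059.

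**3. What the power refers to.** The chance of 13 or more successes is 0.867 at π = 0.80; that is power to reject 0.50. The chance of 18/18, the only result that excludes 0.80, is 0.80^18 = 0.018, 0.90^18 = 0.150 and 0.95^18 = 0.397 at true rates of 0.80, 0.90 and 0.95.

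**4. How often the cut-off is passed below 0.80, ignoring any early stop.** P(X ≥ 13) is 0.209 at π = 0.60, 0.534 at 0.70 and 0.718 at 0.75.

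**5. The two-failure stop.** A cut-off of 13 allows 18 − 13 = 5 non-successes. If π is treatment success and every non-success is a failure, a study that completes under Sections 7.10 and 12.7 would essentially show 17/18 or 18/18. The chance of 17 or more is π^17 × (18(1 − π) + π): 0.001 at 0.60, 0.014 at 0.70, 0.039 at 0.75 and 0.099 at 0.80. The step 4 figures therefore do not describe a trial run under that stop.

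**The case against.** Rejecting p0 and concluding p1 is common shorthand for this class of design. Section 6.2 names the design and states both hypotheses, so a statistician will see 0.80 as the design alternative. The sentence justifies a sample size and is not an analysis instruction. This stands, and it is why the fault is modest. It does not remove the fault, because shorthand is harmless only where the analysis section gives the actual rule, and Section 12 gives none.

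A reader might infer that the trial will report a success rate of at least 80% from 13/18. The documents do not support that: no section directs such a report, and calling π a success rate is itself an assumption. If π is treatment success, the stop at two failures would also normally prevent a completed 13/18, apart from non-successes scored as indeterminate under Section 7.8.

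A reader might also take the pass probabilities in step 4 as the trial's false-positive rate. They are not. The stated 0.05 applies to rejecting π ≤ 0.50, and it is met. The plan claims no 5% control at 0.80.

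Finally, 15/18 to 17/18 have observed rates above 0.80, and results from 11/18 to 17/18 have two-sided 95% exact intervals that contain 0.80. It would be too strong to say that nothing below 18/18 speaks for 0.80. The statement holds only under a stated criterion, here a one-sided 95% lower bound above 0.80, which the plan does not set.

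**Conclusion.** The point holds as a modest fault of interpretation. The sample size of 18 is correct and should not be read as an error. What is wrong is the conclusion tied to rejection: a pass at 13/18 shows π > 0.50 (lower bound 0.502), and the power belongs to that statement. Even 17/18, the lower of the two results that the two-failure stop would essentially leave if π is treatment success, does not exclude 0.80 (lower bound 0.762, p = 0.099).

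This rests on a one-sided 5% level, exact binomial calculation and 18 subjects in the denominator. The inference fault does not depend on which proportion π is. The clash with the stopping rule arises only if π is treatment success.

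**What to change.** Reword Section 6.2 along these lines: 18 subjects give 87% power (13 or more of 18, exact one-sided alpha 0.048) to reject π ≤ 0.50 if the true π is 0.80; rejection supports π > 0.50 only. In the same section, name the proportion that π refers to.

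In Section 12, report that proportion with an exact Clopper-Pearson interval and base any statement about 0.80 on its lower bound. State the level. The one-sided 95% bound, which is the lower limit of a two-sided 90% interval, matches the test. A two-sided 95% interval at 13/18 starts at 0.465 and would seem to contradict a rejection.

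If π is treatment success, Sections 6.2, 7.10 and 12.7 must be reconciled, since a cut-off that allows five non-successes and a stop at two failures do not fit together as written.

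The cost is protocol wording and one interval. No patients are added. The downside is that the stated conclusion becomes less favourable.

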6.3. Expected Duration of Subject Participation

The duration of subject participation from signing the informed consent form will be up to 14 months (includes screening period (1 Day), study IV drug administration (approximately 5-14 Days), Standard of Care Oral Drug Administration (4-5 weeks) (**the total maximum treatment period is typically 6 weeks**), and a follow-up visit 12 months after the last dose of study drug). Baseline assessments for study eligibility will occur within 24 hours before the first dose of study drug. A minimum of 2 days (48 hours) of study drug administration is required.

